Participants will receive a link to a dietary recall questionnaire (Intake24, <https://intake24.co.uk/>) via email the next morning after taking part in the study, which they will be prompted to complete before midnight that day. They will be asked to provide as much detail as possible on what they had for dinner, snacks, and drinks after the restaurant visit. Based on this information and salt values calculated by Intake24, we will estimate the total salt consumed by the participants for the rest of the day after the visit.

Other macronutrient intake

Total kcal, sugar, and saturated fat intake [i.e., other nutrients that are not the main warning focus] will be calculated based on the nutritional content of the order of the participant.

Additional measures

Food choice motives

The “health” subsection of the Food Choice Questionnaire (29) will be used to measure the extent to which health motives may influence participants’ food choices. The subsection consists of 6 items, e.g. “It is important to me that the food I eat on a typical day....is nutritious” answered on a 4-point Likert scale ranging from “Not at all important” to “Very important”. We will calculate the mean response for the six items.

Aim guessing

Participants are told that the study is about dining habits in restaurants. At the start of the post-meal assessments, participants will be asked what they think the aims of the study were (free text response). Any participant that guesses the study aims to be investigating the influence of food warning labels on food choice will be coded as being aware of study aims. One researcher will code awareness of aims ([name]) and a second researcher will independently verify the coding.

Study flow

Recruitment	
 - Participants will be recruited via online adverts, word of mouth, and an existing participant database maintained by researchers at the University of Liverpool. - A link to the screening questionnaire will be provided. (Appendix A) - Participants will be stratified by SEP, age, and sex. 				

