Reimbursement	
 - Participants will receive £25 which will likely cover their lunch costs and serve as an incentive for people from different SEP strata to participate. Participants will either (i) pay for their own meal at the restaurant and receive £25 via invoice or (ii) have their meal paid for by a researcher using a prepaid card; if this costs less than £25, they can request to receive the remaining amount via invoice, if this costs more than £25, they will need to pay the difference at the restaurant. 	

Statistical analysis

Participant characteristics

Participant characteristics will be presented overall and by experimental condition in a table. Data will include age, gender, ethnicity, highest educational qualification, employment status, BMI, frequency of eating OOH, and hunger. Continuous variables will be summarised as means and standard deviations, and categorical variables will be summarised as counts and percentages.

Measured variables

Primary

A linear regression will be used to assess differences between menu conditions in terms of PME. The between-subjects predictor will be label condition, and the dependent variable will be PME.

Highest education level (categorical: NQF level 4 or above, NQF level 3 or below) will be included as a covariate in the model to account for stratification (30). Health motives (continuous) will be included as a covariate as this may predict outcomes (e.g., health motivated individuals may be more likely to believe a menu with labels will change their behaviour) (30). Age and gender will also be included as covariates as previous work suggests that this can influence ratings of label PME and salt intake (13).

Descriptive analysis will be used to report (overall and by condition) participants' label awareness, salt awareness, perceived knowledge gain, perceived influence, and policy support (dichotomised into support/oppose). Logistic regressions will be performed to assess the odds of (i) being aware of the label, and (ii) being aware of the salt content of the meals in the labelled menu group, using the control menu group as the reference category. The same covariates as above will be included.

Secondary

Linear regressions will be performed to assess differences in menu conditions in terms of total salt purchase and total salt intake. The same covariates as above will be included.

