A logistic regression will be performed to assess the odds of selecting a high salt meal in the labelled menu group, using the control menu group as the reference category. The same covariates as above will be included.

As some participants are likely to bring guests to the restaurant and guest tables are the unit of randomization, there may be clustering for outcome variables (i.e., the variation in PME and/or salt purchase/intake may be partially explained by table). We will test for clustering effects by comparing the within-table variability for outcome variables to the between-table variability. We will use the likelihood ratio test to ascertain the difference in likelihoods between the two. If this is statistically significant ($p < .05$) then there is enough evidence to suggest that there is a clustering effect of table groups eating together. If there is evidence of clustering then we will perform a series of linear mixed model analyses, with label condition as an independent variable, and table group as a random effect for primary and secondary outcomes.

Exploratory analyses

Linear regressions will be performed to assess differences in menu conditions in terms of later salt intake, and intake of other macronutrients. This is to examine whether individuals engage in any compensatory eating behaviour after seeing the labels (e.g., they are aware that they consumed a

high salt meal and therefore reduce their salt intake later in the day), or whether intake of other macronutrients (e.g., calories) is impacted. Again, the same covariates as above will be included.

Sensitivity

Sensitivity analyses will be conducted to test if results are the same after removing any participants that correctly guess the aims of the study (i.e., the effect of salt warning labels on food choice, or similar). If many participants identify the study aims (e.g., > 25%) we will examine if study aim awareness status moderates any effects of labelling by including this as a covariate (categorical) in analyses. Any deviations in findings from the main analyses will be reported.

Missing data

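### The planned check on whether aim awareness moderates the label effect enters awareness only as a covariate, which cannot estimate or test moderation

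*Combined protocol and SAP*

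**What the plan says.** The Sensitivity section of the combined protocol and SAP describes two analyses of aim guessing.

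- The first has no trigger. It will "test if results are the same after removing any participants that correctly guess the aims of the study".
- The second runs only if many participants identify the aims, with more than 25% given as the example. It asks whether aim awareness "moderates any effects of labelling by including this as a covariate", the covariate being categorical.

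Departures from the main findings are to be reported.

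Under Measured variables, Primary, the main model is a linear regression: "The between-subjects predictor will be label condition, and the dependent variable will be PME". Education level "will be included as a covariate in the model to account for stratification". Health motives, age and gender enter in the same way, and the later models reuse this set. No interaction or product term is specified anywhere in the plan.

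The Aim guessing section codes as aware anyone who "guesses the study aims to be investigating the influence of food warning labels on food choice". The coding comes from a free-text answer at the start of the post-meal questionnaire. In Appendix E that question precedes the PME items and the labelled menu image that both arms are shown.

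**The concern.** The question and the model do not match. Moderation means that the label effect differs between aware and unaware participants. A model with label and awareness as separate terms has a single label coefficient for both groups, so no parameter in it represents that difference. An analyst who follows the text would have only two outputs to read as moderation, and neither measures it: the awareness coefficient, and the change in the label coefficient after adjustment.

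Timing makes the second output harder to read. Awareness is recorded after participants have ordered and eaten, and it means guessing an aim about warning labels. Participants are told that the study concerns dining habits, and controls see no labels before they answer. Awareness is therefore probably more common in the labelled arm and partly a result of the label. The adjusted label coefficient can then move without any moderation, and without confounding of the randomised comparison.

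At stake is how the report describes the role of demand effects if aim guessing turns out to be common.

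**Working it through.** **The plan's own figure.** Inputs from Sample size: d = 0.35, 80% power, two-tailed. Alpha is .05, from Multiple comparisons. Per arm, n = 2(1.960 + 0.842)² / 0.35² = 2 × 7.85 / 0.1225 = 128.1, so 129 (258 in total). The t-test version gives 129.1, so 130 per arm and 260 in total, with power 80.3%. The stated 260 is reproduced. The point does not depend on it.

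**1. What the covariate model contains.** Write outcome = a + b·label + c·aware. The label effect is b in unaware participants and (a + b + c) − (a + c) = b in aware participants, so the difference between them is zero by construction. Adding d·label × aware makes the two effects b and b + d. Moderation is d, and the stated model has no d.

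**2. Equal awareness.** Assumed: label effects of 0.15 SD (unaware) and 0.75 SD (aware), with 40% aware in each arm. The single coefficient is 0.6 × 0.15 + 0.4 × 0.75 = 0.39 SD, with or without the covariate. The five-fold difference does not appear in this model.

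**3. Unequal awareness.** Same assumed effects, no effect of awareness among controls, 130 per arm, 50% aware (labelled) and 5% aware (control). Overall awareness is 27.5%, above the example trigger.

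- Unadjusted: 0.5 × 0.75 + 0.5 × 0.15 = 0.45 SD.
- The covariate model weights each stratum by n₁n₀/(n₁ + n₀). Aware: 65 × 6.5 / 71.5 = 5.9. Unaware: 65 × 123.5 / 188.5 = 42.6.
- Adjusted: (5.9 × 0.75 + 42.6 × 0.15) / 48.5 = 0.22 SD, a fall of about 0.23 SD.

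**4. Nearly the same fall with no moderation.** Keep 50%/5%. Assume a label effect of 0.35 SD in both strata, and that aware participants score 0.5 SD higher in both arms. Unadjusted: 0.35 + 0.5 × (0.50 − 0.05) = 0.575 SD. Adjusted: 0.35 SD. The fall is 0.225 SD with d = 0, so the size of the shift does not distinguish moderation from its absence.

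**5. The awareness coefficient does not track moderation either.** Simulations with N = 260, 25% aware in both arms and 3,000 replicates:

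- No moderation, awareness worth 0.5 SD: the awareness term is significant in 93% of runs and the interaction in 5.5%.
- Moderation of 0.7 SD (label effect 0.175 unaware, 0.875 aware), with awareness netting to zero overall: the awareness term is significant in 5.8% of runs and the model returns one label effect of 0.35 SD. The interaction model recovers about 0.69 SD and rejects in 67%.

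**6. What an interaction term could deliver.** SE = √(sum of 1/n over the four label-by-awareness cells), with SD 1. Power = Φ(0.35/SE − 1.96). Awareness rates are assumed.

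| Aware, control / labelled | SE, N = 260 | Power for 0.35 SD, N = 260 | Smallest interaction with 80% power, N = 260 | Power for 0.35 SD, N = 500 |
|---|---|---|---|---|
| 25% / 25% | 0.286 | 23% | 0.80 SD | 40% |
| 50% / 50% | 0.248 | 29% | 0.70 SD | 50% |
| 10% / 40% | 0.343 | 17% | 0.96 SD | 29% |

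In the 5%/50% case of step 3, SE = √(1/65 + 1/65 + 1/6.5 + 1/123.5) = 0.44. Power for the assumed 0.60 SD difference is then about 28% (26% by simulation). At the plan's exploratory alpha of .01, replacing 1.96 by 2.576 gives about 9%, 12% and 6% for the three rows at N = 260. Clustering by table would lower all of these.

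**The case against.** The strongest reply is that the covariate step does not stand alone. The exclusion analysis runs whatever the level of awareness. Under the assumed effects it would return about 0.15 SD, against 0.39 or 0.45 SD overall, so a reader would see the effect shrink. A reader might infer that the plan has no working check on demand effects; the documents do not support that. The exclusion analysis bears directly on whether the effect survives without aim-guessers. It does not give the effect in aware participants or a test of the difference, and that is the question the second step poses.

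The authors may also have meant an interaction and worded it loosely. That is plausible, since they name moderation. But the plan uses the term covariate elsewhere for main-effect adjustment and names no product term, so the text as written leads to the wrong model.

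A reader might equate aim awareness with noticing the labels. The plan measures those separately (Label awareness and Aim guessing), and someone can notice a label without guessing the aim. Only the narrower statement stands: awareness is recorded after exposure and is probably more common in the labelled arm.

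An interaction analysis also conditions on this post-exposure variable, so its strata are not randomised comparisons, however many participants they hold. That objection stands and limits what the fix can claim.

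Finally, the effect sizes and awareness rates are assumptions. The documents give none, and they do not say what would be concluded from the covariate model.

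**Conclusion.** The covariate step cannot answer the question set for it. This follows from the form of the model and needs no assumption about effect size. The figures (one 0.39 SD effect hiding 0.15 and 0.75 SD; a coefficient moving from 0.45 to 0.22 SD) are illustrations under assumed effects and awareness rates.

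The scope is narrow: a conditional sensitivity analysis. A reader might infer that the trial's main conclusions are at risk. They are not: the primary and secondary models do not include awareness, and the sample size and interim rule do not depend on it. Nor would an interaction term give a decisive test, given the power of about 17% to 29% at N = 260 and the post-exposure timing. The correction is worth making because the wording would otherwise produce an output that invites misreading.

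**What to change.** Replace the covariate wording in the Sensitivity section with text along these lines:

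> If many participants identify the aims, we will add a label condition × aim-awareness interaction to the main model for each outcome, keeping the table random effect where one is used. We will report the interaction estimate with its 95% confidence interval, the label effect in aware and in unaware participants, and the number aware in each arm, next to the analysis that excludes aim-guessers. This analysis is exploratory in all cases, because awareness is measured after exposure and power is low.

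Add that the label coefficient from a model with awareness as a main effect only will not be taken as evidence on moderation. State also whether the plan's .01 level for exploratory analyses applies, or whether the result will be presented as an estimate without a significance claim.

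The cost is a few lines of SAP text and one extra model term. No new data are needed.

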To date, the impact of nutrient warning labels has not been tested in a real-world randomised controlled trial (i.e., in a restaurant), or in a UK context. Recent work suggests that UK consumers support the introduction of nutrient warning labels, and their PME was rated as significantly higher relative to a control label (QR code) (13). This study aims to test the effect of a menu featuring salt warning labels (design informed by previous work (13)) on perceived message effectiveness relative to a menu with no labels in a real-world restaurant environment. The study will also act as a pilot experiment for examining the impact of the salt warning label on food choice and subsequent salt intake in real-world conditions.

Primary objectives:

- To measure the PME of a menu featuring salt warning labels relative to a menu with no labels
- To measure label awareness, perceived knowledge gain, and perceived influence of the label on food choice

Secondary objectives:

- To identify whether there is an effect of the salt warning label on:
 - Food choice (label/no label)
 - Total salt selected
 - Total salt intake
- To examine support for the introduction of a salt warning label policy in the UK

Experimental design

The study will be a between-subjects randomised controlled trial design. The between-subject factor is the menu labelling. In the experimental condition, a nutrient warning label will be placed next to menu items that are high in salt. In the control condition, there will be no labels. The outcome will be (i) perceived message effectiveness, (ii) salt selected, label (y/n) selected, and salt intake. This will allow us to examine whether the salt warning label intervention impacts perceived message effectiveness and food choice relative to the control condition.

Participants and recruitment

Recruitment

Participants will be recruited via social media adverts (Facebook, Instagram), a database maintained by researchers at the University of Liverpool, and word of mouth. Interested participants will be asked to click a link which will take them to an online screening questionnaire (Appendix A). Participants can bring a maximum of nine guests to the restaurant. Guests will be pre-screened in advance to ensure eligibility. In pre-study instructions participants will be informed that any guests they bring will participate in the study.

Sampling

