Participant groups will be randomised to either the experimental or control condition using a block randomisation schedule (<https://www.sealedenvelope.com/simple-randomiser/v1/lists>). Participants seated at the same table will be in the same condition. Therefore, to adjust for possible differences in group sizes and consequently numbers in each condition, we will randomise in blocks of 50. The menu contains eight main dishes and eight light bites/small plates (five of which are high in salt).

Figure 3: Menu (A) for the control condition

ME NU

EVERYDAY FROM 11.30AM

Light Bites/Small Plates

Mushroom Soup served with crusty bread and butter	£5.50
Cajun Chicken Flatbread Flatbread filled with Cajun Chicken, roasted pepper, herb salad & lime mayonnaise	£7.95
Beetroot Hummus Flatbread Flatbread served with Hummus, house salad & pomegranate dressing	£6.95
Ruban Toasted sandwich Sliced pastrami, Baltic pickles, Sauerkraut with melted Gruyere	£8.95
Mexican Cheese on toast A blend of melted cheese, chillies and spring onion	£5.95
Loaded Dirty Fries Melted cheese, Baltic chilli and BBQ sauce - Add Chicken or Halloumi for £1.50	£5.95
Loaded Dirty Fries with chicken Melted cheese, Baltic chilli and BBQ sauce - Add Chicken or Halloumi for £1.50	£7.45
Loaded Dirty Fries with halloumi Melted cheese, Baltic chilli and BBQ sauce - Add Chicken or Halloumi for £1.50	£7.45

Mains

Chefs Homemade Scouse Served with crusty bread, pickled cabbage and beetroot	£8.50
Steak & Ale Pie Served with house fries and mushy peas	£11.50
Baltic Black & White Burger Black Burger Bun, Grilled Halloumi, peppers, tomato, lettuce, chilli BBQ relish served with house fries	£10.00
6oz Baltic Cheese Burger A 6oz burger patty, Brioche bun, lettuce, tomato served with burger relish & House fries	£10.95
Steak & Eggs Hash Grilled 4oz Ribeye steak, creamy peppered hash potatoes topped with fried egg	£11.50
Super Food Salad Baltic house salad, quinoa, pomegranate, tenderstem Broccoli, cucumber, tomato, red onion served with Soy honey dressing Add Chicken or Halloumi for £1.50	£7.95
Super Food Salad with chicken Baltic house salad, chicken, quinoa, pomegranate, tenderstem Broccoli, cucumber, tomato, red onion served with Soy honey dressing	£9.45
Super Food Salad with halloumi Baltic house salad, halloumi, quinoa, pomegranate, tenderstem Broccoli, cucumber, tomato, red onion served with Soy honey dressing	£9.45

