Information sheet and informed consent	
 - Eligible participants will be e-mailed an information sheet (Appendix B) and consent form (Appendix C). Participants can ask any questions about the study via e-mail. - The researcher will schedule a study visit day, leaving 30-minute gaps between participant groups. Participants may bring a maximum of nine guests aged 18 years or older to the restaurant. - As the guests did not yet receive an online information sheet and consent form, all participants will also be provided with information by the researcher and provide verbal consent. The researcher will answer any questions prior to the study. 				
Meal choice task	
 - Participants will be invited to visit the restaurant. They will be assigned in advance to either the control or experimental condition. Any guests will be in the same condition as the primary participant (i.e., participants will be randomised by table). They will also be given a participant number which they will be required to enter in any questionnaire they complete. 				
	
  
 Control condition	Experimental condition	
   
  
 - Participants will receive a standard menu without nutrient warning labels. 	 
 - Participants will receive a menu featuring a nutrient warning label next to items high in salt. Text at the bottom of the menu will read “[label image] indicates that the salt content of this item is higher than 50% of the daily recommended limit (6g per day). High salt 	
  
	Control condition	Experimental condition	
 - Participants will receive a standard menu without nutrient warning labels. 	
 - Participants will receive a menu featuring a nutrient warning label next to items high in salt. Text at the bottom of the menu will read “[label image] indicates that the salt content of this item is higher than 50% of the daily recommended limit (6g per day). High salt
Control condition	Experimental condition				

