We do not foresee missing data being a problem as when we design measures in Qualtrics all fields will require a response, and all data will be collected by a researcher during the restaurant visit. However, it is possible that some participants will not complete the online questionnaire to assess later intake after the restaurant visit. Any missing data for later nutrient intake will be imputed.

Multiple comparisons

The alpha will be set at .05 for primary and secondary outcome analyses. To adjust for multiple comparisons, the alpha for exploratory analyses alpha will be reduced to .01.

Sample size

The label in the present study (or a similar label) has not previously been tested in a real-world UK context, in terms of PME or food choice. A RCT examining the effects of 'high in' added sugar labels on PME found large effects ($d = 0.58 - 0.63$) (7). A meta-analysis on food labelling found a small effect ($OR = 0.65$, or $d = .24$) of warning labels in terms of reducing consumers' probability of selecting less healthy items (31). However, a RCT examining the effects of 'high in' sodium labels on salt (g) and 'high in' item choice found very small effects ($d = 0.03$ and 0.04 respectively) (9), but there are important methodological differences (e.g., menu size) between this study and the present study. The primary purpose of the present study is to examine PME, so we will therefore power the study for this primary outcome, but in doing so we will have reasonable power to detect small-medium effects for our secondary outcome (food choice).

In the present study, G power calculation indicates a minimum sample of 260 participants (130 per condition) will provide sufficient power (80%, two-tailed) to detect small-medium between condition effects ($d = 0.35$) of the salt warning label on PME, salt purchased, and salt intake using between-subject ANOVAs (as planned).

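### The 80% power stated for 260 participants assumes independent people and carries no design effect, although whole tables are randomised

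*Combined protocol and SAP*

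**What the plan says.** The Sample size section says that "a minimum sample of 260 participants (130 per condition) will provide sufficient power (80%, two-tailed) to detect small-medium between condition effects". The effect is d = 0.35, the test is a between-subject ANOVA, and the claim covers PME, salt purchased and salt intake together. The Multiple comparisons section adds: "The alpha will be set at .05 for primary and secondary outcome analyses".

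The design sections describe a different unit. Under Recruitment, "Participants can bring a maximum of nine guests to the restaurant", so a table can hold ten. Under Intervention, "Participants seated at the same table will be in the same condition". The Study flow table (Meal choice task) confirms that "participants will be randomised by table". The Secondary part of the Statistical analysis section recognises the consequence: "guest tables are the unit of randomization, there may be clustering for outcome variables". It responds only in the analysis, after a likelihood ratio test: "If there is evidence of clustering then we will perform a series of linear mixed model analyses".

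No section gives a mean table size, a spread of sizes, an ICC or a design effect.

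**The concern.** When tables are allocated as a unit and people at one table resemble each other, 260 people carry less information about the treatment contrast than 260 independent people. A calculation that treats them as independent then overstates power for any test that holds its 5% level. Diners at one table may well order alike, and the plan itself names PME and salt purchase or intake as outcomes that table may partly explain.

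The figure matters because 260 is both the stated minimum and the point of the interim analysis, and data collection may stop there. A reader who takes the 80% at face value would read too much into a non-significant salt result.

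**Working it through.** **Step 1: reproduce the plan's figure.** Inputs from the Sample size section: d = 0.35, 130 per arm, two-sided test. Alpha 0.05 comes from Multiple comparisons. For independent people, the noncentrality is d × sqrt(N/4) = 0.35 × sqrt(65) = 2.82 on 258 degrees of freedom. The noncentral t distribution gives:

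- 130 per arm: 80.27%
- 129 per arm: 79.97%

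So 260 is the smallest even total that reaches 80%. The sum is right for independent people and nothing is left over: power drops below 80% once the design effect passes about 1.007.

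**Step 2: allow for tables.** With mean table size m and CV of table size:

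- design effect DE = 1 + ((1 + CV²) × m − 1) × ICC
- effective N = 260 / DE
- degrees of freedom = number of tables − 2 = 260/m − 2

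All of m, CV and ICC are assumptions, because the documents give none. I take m from 1.5 to 4, CV 0.5 and ICC from 0.01 to 0.20.

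Worked case, m = 3 and ICC 0.10: DE = 1 + (1.25 × 3 − 1) × 0.10 = 1.275. Effective N = 260/1.275 = 204. The noncentrality is 0.35 × sqrt(204/4) = 2.50 on about 85 degrees of freedom. Power is 69.5%, and the effect detectable with 80% power is d = 0.40.

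Power at 260, d = 0.35, before any covariate gain:

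| ICC | m = 1.5 | m = 2 | m = 3 | m = 4 |
|---|---|---|---|---|
| 0.01 | 79.8% | 79.4% | 78.6% | 77.8% |
| 0.05 | 78.4% | 77.1% | 74.4% | 71.8% |
| 0.10 | 76.8% | 74.3% | 69.5% | 65.1% |
| 0.20 | 73.5% | 69.0% | 61.1% | 54.4% |

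Over this grid the detectable effect runs from d = 0.35 to d = 0.47.

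**Step 3: allow for covariates.** The planned models adjust for education, health motives, age and gender, but no R-squared is assumed anywhere. With an assumed R-squared of 0.10, d becomes 0.35/sqrt(0.9) = 0.369. I keep the same ICC for the residuals, which is a further assumption. The grid then runs from 58.8% to 83.8%. Seven of the 16 cells reach 80%: all four sizes at ICC 0.01, sizes 1.5 and 2 at ICC 0.05, and size 1.5 at ICC 0.10. The worked case (m = 3, ICC 0.10) rises to 74.0%.

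**Step 4: PME at the effect the plan cites.** The Sample size section cites d = 0.58 to 0.63 for PME. At d = 0.58 and 260 participants, power over the Step 2 grid is 93.0% to 99.6%.

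**The case against.** Four points can be made for the plan.

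- **Clustering is already handled.** The conditional mixed model concerns the analysis. It makes the standard error reflect the clustering and does not restore the lost information, so it does not support the 80%.
- **The planned models are adjusted.** "Health motives (continuous) will be included as a covariate as this may predict outcomes", along with education, age and gender. This stands in part. Step 3 shows that a modest R-squared brings some small-table, low-ICC cases back to 80%. But the plan does not quantify the gain, and the stated 80% is not derived from it.
- **The size of the loss is assumed.** This stands. The maximum of nine guests says nothing about the mean, and the plan expects only that some participants will bring guests. At ICC 0.01 the loss is at most about 2.5 points. The 54% end needs tables averaging four with ICC 0.20.
- **Consequences are small.** This largely stands for PME, given Step 4, and the study is described as a pilot for food choice and salt intake. But 80% at d = 0.35 is claimed for salt purchased and salt intake as well. The sodium-label trial cited in the same section found d = 0.03 for salt, so those outcomes have no such margin, even though the plan notes differences in method from that trial.

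Two stronger readings are tempting. A reader might infer that the sample size was miscalculated; it reproduces exactly, and what is missing is the clustering assumption. A reader might also infer that the planned analysis must fall short of 80%, or that 260 is too few. The documents do not establish this, because table size, ICC and covariate R-squared are all unknown.

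**Conclusion.** The 80% is wrong as written for this design. It holds for independent people, with room for a design effect of only about 1.007, while the trial randomises tables and expects clustering. Before covariate gain, any non-trivial intra-table correlation puts power for all three outcomes, at a valid 5% level, below the stated figure.

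The structural mismatch is certain. The size of the shortfall is not: it ranges from almost nothing to about 26 points (80.3% − 54.4%) over assumed inputs, and covariates could remove it where tables are small and the ICC is low. The practical weight falls on the salt outcomes. PME keeps a wide margin if the effect is near the cited 0.58.

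A reader might also infer that the possible extension to about 500 settles the matter. It does not: that size is reached only conditionally on the interim result, and the interim rule looks at PME and high-salt meal selection, not at salt purchased or salt intake.

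**What to change.** In the Sample size section, say that the 80% ignores clustering. State the sponsor's assumed mean table size, CV of size and ICC, with a range that includes small tables and low ICC. Apply 1 + ((1 + CV²) × mean size − 1) × ICC, and replace the flat 80% with the resulting power and detectable effect at 260. Possible wording, with placeholder inputs for the sponsor to replace:

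> Tables are randomised. Ignoring clustering, 260 participants give 80% power at d = 0.35. With a cluster-adjusted analysis and an assumed mean table size of 3, CV 0.5 and ICC 0.10 (design effect 1.28), before covariate gain, 260 participants give about 70% power at d = 0.35 and 80% power at d = 0.40. Over mean sizes 1.5 to 4 and ICC 0.01 to 0.20, power at d = 0.35 is 54-80%, or 59-84% if covariates explain 10% of the variance.

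Do not add power figures computed as if the sample were fixed at about 500, because that size depends on the interim result.

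The cost is one paragraph of wording. Recruitment, conduct and analysis stay as they are. The downside is a less favourable stated power.
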